9.4 Interim Analyses and Stopping Guidelines

Interim analyses and/or stopping for unexpected efficacy: Since the trial involves low-risk behavioral interventions that are of limited duration, the investigators believe that there is no scientific or ethical reason to stop the trial early or alter the trial design if treatment appears to be more effective than expected. Thus, as long as no safety issues arise, the trial will not be stopped or altered if the therapeutic intervention appears unexpectedly effective.

Interim analyses and/or stopping for harm: Although this study involves low-impact behavioral interventions that are not expected to pose a significant risk to participant safety, consideration may be given to stopping the trial early if unexpected and clinically significant adverse effects occur in either intervention group that may endanger the safety of participants. These may take the form of SAEs or non-serious AEs posing a substantial safety risk and warranting early termination of the trial. If evidence of adverse effects emerges, the investigators in consultation with the DSM may determine that these side effects are minor and the study can continue as planned, or may decide to alter or stop the study to prevent these side effects.

Interim analyses and stopping for futility: Consideration may be given to stopping the trial if recruitment and retention are so poor that the ability to meet recruitment goals or meet retention thresholds is severely compromised. For example, consideration will be given to stopping this study prior to its scheduled completion if recruitment falls more than 30% below planned rates and/or timely follow-up (i.e., completion of study visits within recommended windows) falls below 70%.

9.5 Outcomes

9.5.1 Primary Efficacy Outcome

The primary efficacy outcome will be change in the average frequency of any urinary incontinence over 12 weeks based on a validated 3-day voiding diary. To that end, frequency of incontinence will be assessed based on voiding diaries completed at screening/baseline, 6 weeks, and 12 weeks. If improvement in incontinence is observed over 12 weeks, additional analyses may explore persistence of benefits 12 and 24 weeks after the completion of the yoga or stretching/strengthening programs.

9.5.2 Secondary Efficacy Outcomes

Secondary efficacy outcomes will include change in the frequency of stress-type, urgency-type, daytime, and nighttime incontinence, also assessed using validated voiding diaries, over 12 weeks. The total number of any, stress-type, and urgency-type incontinence episodes will be calculated for each diary and then divided by the total number of days of recording to calculate the average number of incontinence episodes per day of each type.

Other secondary efficacy outcomes will include change in quality-of-life outcomes associated with incontinence over 12 weeks. To that end, changes

in depression and anxiety symptoms and incontinence-related quality of life will be assessed using validated questionnaires completed at screening/baseline, 6 weeks, and 12 weeks, as well as 12 and 24 weeks after the completion of yoga or control programs.

9.6 Data Analyses

9.6.1 Analyses to address main objectives

Objective 1: To determine the efficacy of a group-based yoga intervention in reducing the frequency of urinary incontinence in ambulatory midlife and older women.

Hypothesis 1A: Ambulatory incontinent women randomized to the yoga intervention will demonstrate at least a 20% greater decrease in total incontinence frequency (measured by validated voiding diaries) over 12 weeks, compared to women randomized to the control intervention.

Hypothesis 1B: If improvements in total incontinence frequency are observed at 12 weeks, these improvements will be sustained 12 and 24 weeks after the end of the intervention programs.

Planned analyses: Intervention effects on the primary outcome of total incontinence frequency will be estimated using a linear mixed model (LMM) for changes since baseline in the overall frequency of any incontinence episodes at 6 and 12 weeks, adjusting for baseline incontinence frequency. Analyses will be by intention to treat, according to intervention group assignment, and without regard to adherence to intervention classes or practice. The LMM will account for clustering using nested random effects for group intervention class series and individual participant. In addition to fixed effects for study location and type of incontinence, the LMM will include terms for intervention, time, and the time-by-intervention interaction, thus allowing for secular trends in controls, as well as different intervention effects at 6 and 12 weeks. The intervention effect will be summarized by an orthogonal contrast capturing any linear trend across 6 and 12 weeks; this makes use of information for participants with 6 but not 12 week outcomes. If the yoga intervention appears effective over 12 weeks, we will also assess maintenance of effects over time, by comparing changes since baseline at 12 weeks with those at 24 and 36 weeks, using an additional LMM. Intervention effects will again be summarized by an orthogonal contrast for linear trend across the three time points.

Objective 2: To determine the efficacy of a group-based yoga intervention in reducing the frequency of type- and context-specific urinary incontinence in ambulatory middle-aged and older women.

Hypothesis 2A: Ambulatory incontinent women randomized to the yoga intervention will report decreases in the frequency of stress-type, urgency-type, daytime, and nighttime incontinence (also measured by voiding diaries) over 12 weeks, compared to women randomized to the control intervention.

Hypothesis 2B: If improvements in stress-type, urgency-type, daytime, and nighttime incontinence frequency are observed at 12 weeks, these improvements will be sustained 12 and 24 weeks after the end of the intervention programs.

Planned analyses: For additional confirmation of effects on the primary outcome of total incontinence frequency, we will examine effects on frequency of urgency

incontinence episodes and stress incontinence episodes, again using the modeling approach indicated above. Additional models will explore effects on frequency of daytime and nighttime incontinence.

Objective 3: To determine the efficacy of the yoga intervention in improving incontinence-related functioning and quality-of-life.

Hypothesis 3A: Ambulatory incontinent women randomized to the yoga intervention will report greater improvements in condition-specific functioning and quality of life (assessed by validated questionnaires) over 12 weeks, compared to women randomized to the control intervention.

Hypothesis 3B: Compared to women randomized to the control intervention, we hypothesize that women randomized to the yoga intervention will report sustained improvements in condition-specific quality of life 12 and 24 weeks after the end of the intervention programs.

Planned analyses: Additional LMMs will examine other secondary outcomes including incontinence-related quality of life as assessed by validated questionnaires (i.e., the Incontinence Impact Questionnaire (IIQ), Urogenital Distress Inventory (UDI), Patient Perception of Bladder Condition (PPBC), Pelvic Organ Prolapse/Incontinence Sexual Questionnaire, and IUGA-Revised (PISQ-IR) questionnaire), as well as depression and anxiety symptoms assessed by additional questionnaires (i.e., the Center for Epidemiology Studies Depression Scale (CES-D), Hospital and Anxiety Depression Scale (HADS), and State Trait Anxiety Inventory (STAI)). We will again estimate intention-to-treat intervention effects, adjusting for study location, using the same modeling strategy as for objective 1. Transformation or categorization of questionnaire scores (in combination with logistic or proportional odds models) will be considered as needed to deal with skewness of outcomes.

Objective 4: To explore whether the yoga intervention is associated with improvements in 1) pelvic floor muscle strength, 2) peripheral autonomic function, and/or 3) lower extremity physical function, and assess whether improvements in these factors may mediate improvement in incontinence.

Hypothesis 4A: Among ambulatory incontinent women enrolled in this trial, the yoga intervention will be associated with improvements in a) pelvic floor muscle strength (assessed by pelvic exam), b) cardiac autonomic function (assessed by heart rate variability and impedance cardiography), and c) lower extremity physical function (assessed by physical performance assessment) over 12 weeks.

Hypothesis 4B: Among ambulatory incontinent women enrolled in this trial, changes in incontinence frequency over 12 weeks will be partly mediated by changes in a) pelvic floor muscle strength, b) cardiac autonomic function, and c) lower extremity physical function.

Planned analyses: Additional intermediary outcomes include pelvic floor muscle strength (measured by Brink scale), peripheral autonomic function (reflected by respiratory sinus arrhythmia [RSA] and cardiac pre-ejection period [PEP] parameters), and lower extremity physical function (assessed using the Short Physical Performance Battery [SBBP] and 2-minute step test). Intervention effects will first be estimated using LMMs, using the same modeling strategy used for objectives 1-3. Next, to assess for mediation of changes in incontinence frequency by changes in these factors, we will assess correlation between changes in these

parameters and change in incontinence frequency between baseline and 12 weeks. We will then examine attenuation of intervention effects estimates from the primary intention-to-treat analyses after adjustment for these potential mediators. Mediators will initially be analyzed as continuous variables (i.e., continuous change in RSA and PEP), but categorization will be considered in the event of skewed variable distributions. If evidence of mediation is observed, we will estimate 95% bias-corrected percentile confidence intervals for the proportion of intervention effect explained, using resampling by participant to fully account for the correlation between intervention effect estimates before and after adjustment for change in the mediators

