9.2 Sample Size

Sample size has been calculated based on parameter estimates derived from both the investigators' past pilot studies on yoga as well as other group-based incontinence intervention trials conducted by study team members.¹⁰³ Assumptions include: a) average baseline frequency of incontinence of ~23-24 episodes/week; b) standard deviation (SD) of change in incontinence frequency of ~14.4; c) correlation between outcome values of ~0.59; and d) loss of ~15% by 3 months. Assuming a ~50% decrease in incontinence frequency among controls (which is the threshold at which women with daily incontinence start to perceive meaningful benefit from treatment¹⁸), the team will power the study to detect a between-group difference in reduction in incontinence of at least 20% in the yoga versus stretching/strengthening control group (corresponding to a \geq 70% reduction in frequency of incontinence in the yoga group) at 3 months. Under these assumptions, a sample size of 240 (120 per group) will provide 80% power in 2-sided tests with 5% type-I error to detect a between-group difference in reduction in the primary outcome of total incontinence frequency of at least 20% in the yoga vs. control arm. With regard to secondary outcomes, this sample will also provide 80% power to detect moderate between-group differences of 0.26 to 0.39 SDs, assuming intraclass correlation of outcomes in the range of 0.4-0.8.

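### Section 9.6.1 leaves the within-participant covariance of the 12/24/36-week maintenance model unspecified; if it is only a random intercept, the trend standard error is too small when correlation falls with time

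*Combined protocol and SAP*

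**What the plan says.** Section 9.6.1 (Objective 1) plans a linear mixed model for "changes since baseline in the overall frequency of any incontinence episodes at 6 and 12 weeks, adjusting for baseline incontinence frequency". On dependence it says: "The LMM will account for clustering using nested random effects for group intervention class series and individual participant". The effect is summarised by a linear-trend contrast over weeks 6 and 12.

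If yoga appears effective, maintenance is assessed "by comparing changes since baseline at 12 weeks with those at 24 and 36 weeks, using an additional LMM", and "Intervention effects will again be summarized by an orthogonal contrast for linear trend across the three time points". For these contrasts section 9 names no random slope, residual covariance structure or robust variance. Section 9.6.1 reuses the Objective 1 modelling for Objectives 2 and 3.

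On the standing of the analysis, section 9.5.1 is conditional: "additional analyses may explore persistence of benefits 12 and 24 weeks after the completion of the yoga or stretching/strengthening programs". The Précis nevertheless lists persistence among the additional secondary outcomes, and hypotheses 1B, 2B and 3B concern it.

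Section 9.2 gives "correlation between outcome values of ~0.59" and "standard deviation (SD) of change in incontinence frequency of ~14.4", and for secondary outcomes a power statement "assuming intraclass correlation of outcomes in the range of 0.4-0.8". None of these says how correlation changes with the gap between visits.

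**The concern.** A participant random intercept with independent residuals implies compound symmetry: the same variance at every visit and the same correlation for every pair. Weeks 12, 24 and 36 are equally spaced, so the linear-trend contrast has weights −1, 0, +1. Its true variance depends on the correlation between weeks 12 and 36, the pair furthest apart. The fitted model uses the average over the three pairs instead. If the distant pair is less correlated than the adjacent pairs, the model understates the variance.

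What is at stake is the interval for how the arm difference changes between the end of the classes and 24 weeks later. An interval that is too narrow makes a false claim of fading or growing benefit more likely than 5%. It also makes an exclusion of fading look firmer than the data allow.

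**Working it through.** **1. The plan's own figure.** Take baseline 23 episodes/week (9.2), so 20% is 0.20 × 23 = 4.6. The baseline-adjusted SD is 14.4 × √(1 − 0.59²) = 14.4 × √0.6519 = 11.63. Per arm, n = 2 × (1.96 + 0.84)² × 11.63² / 4.6² ≈ 2 × 7.85 × 135.2 / 21.16 = 100.3, rounded up to 101. Then 101/0.85 = 118.8, or 119 per arm and 238 in total, against the stated 240. With 102 completers per arm (120 × 0.85) power is 80.7%. Baselines of 23.5 and 24 give 230 and 220. The sample size is therefore reproduced. It concerns the 12-week comparison and uses no correlation between weeks 12, 24 and 36. The plan states no standard error or power for the maintenance contrast.

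**2. Formulas for three visits (equal variances, complete data).** Let r̄ be the mean of the three pairwise correlations.
- True variance of the arm difference in change from week 12 to week 36: (2/n) × 2s² × (1 − r₁₂,₃₆).
- Variance used by the random-intercept model: (2/n) × 2s² × (1 − r̄).
- Ratio of model to true standard error: √[(1 − r̄)/(1 − r₁₂,₃₆)].
- Actual two-sided type I error: 2 × [1 − Φ(1.96 × ratio)].

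The ratio does not depend on s or n. To show standard errors, s = 14.4 is assumed at every visit, with 90 per arm at week 36 (120 × 0.75, from the dropout limit of 25% in 9.6.2).

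**3. Worked case.** First-order autoregressive decay from 0.59 gives r₁₂,₃₆ = 0.59² = 0.348 and r̄ = (0.59 + 0.59 + 0.348)/3 = 0.509. The ratio is √(0.491/0.652) = 0.87. Since 1.96 × 0.8675 = 1.70, type I error is 8.9%.

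**4. Range.** All correlation patterns are assumptions.

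| Correlations 12–24 / 24–36 / 12–36 | r̄ | Model SE | True SE | Ratio | Type I error |
|---|---|---|---|---|---|
| 0.59 / 0.59 / 0.59 | 0.590 | 1.94 | 1.94 | 1.00 | 5.0% |
| 0.59 / 0.59 / 0.55 | 0.577 | 1.98 | 2.04 | 0.97 | 5.7% |
| 0.59 / 0.59 / 0.50 | 0.560 | 2.01 | 2.15 | 0.94 | 6.6% |
| 0.59 / 0.59 / 0.35 (autoregressive) | 0.509 | 2.13 | 2.45 | 0.87 | 8.9% |
| 0.40 / 0.40 / 0.16 (autoregressive) | 0.320 | 2.50 | 2.78 | 0.90 | 7.8% |
| 0.80 / 0.80 / 0.64 (autoregressive) | 0.747 | 1.53 | 1.82 | 0.84 | 10.0% |
| 0.55 / 0.55 / 0.59 (reverse) | 0.563 | 2.01 | 1.94 | 1.03 | 4.3% |

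A simulation of 20,000 complete-data trials per case, 90 per arm, gave type I error of 5.2% for equal correlation, 6.6% for the 0.50 case, and 9.2% for autoregressive 0.59 (mean model SE 2.12, empirical 2.46).

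**5. The two-visit model.** With visits at 6 and 12 weeks there is one within-person difference. The random-intercept residual variance is estimated from it, so the ratio is 1.00 for that difference, and likewise for the sum, even if the two variances differ. Contrasts that weight the visits unequally, including a single visit, use the pooled variance and go wrong only if the variances differ. As an illustration, assume residual SDs of 13 at week 6 and 10 at week 12. The pooled variance is (169 + 100)/2 = 134.5, and the week-6 ratio is √(134.5/169) = 0.89. The closed test of change from baseline to 6 weeks (9.6.2) would then run at 8.0%. The week-12 ratio is √(134.5/100) = 1.16, which is conservative. Neither SD comes from the documents.

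**The case against.** The strongest reply is that the plan does not specify a wrong covariance; it leaves one unstated. The sentence on random effects belongs to the 6/12-week model and does not mention intercepts or independent residuals, so a random slope or a structured residual could still be chosen for the three-visit model. This is correct, and it is why the point is framed as a gap. In the two-visit model, though, a random slope plus residual cannot be identified: two visits supply three variances and covariances, and the model needs four parameters. An intercept is therefore the natural reading, and nothing else is named for the later model.

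Second, the decay is assumed. This stands. With equal correlation there is no error, and with the reverse pattern the standard error is slightly too large. The 0.4–0.8 range in 9.2 is a power assumption for secondary outcomes and is not evidence of decay.

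Third, the analysis is conditional and has no stated alpha or power. This limits the consequence, but persistence is still a listed secondary outcome with numbered hypotheses.

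A reader might go further and infer two things that the documents do not support:
- **That the primary error rate or power is wrong.** The stated summary is a trend across two visits. Taken as their difference, it has the correct variance, and 240 is unaffected.
- **That all Objective 4 measures share the problem.** Autonomic measures and pelvic floor strength are taken only at baseline and 12 weeks (6.1.6, 6.1.7, 6.2.7), so there is no between-visit covariance to get wrong. Physical performance testing stops at 12 weeks, so it has no maintenance contrast.

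**Conclusion.** The point holds in a conditional form. The covariance for the 12/24/36-week model is not stated, and its plainest reading gives a trend standard error that is too small if correlation falls with time between visits. Over the decay patterns tried, the shortfall is about 3% to 16%, with type I error from 5.7% to 10.0%; the two patterns closest to the plan's single value of 0.59 that serve as reference cases give 6.6% and 8.9%.

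This rests on a random-intercept reading, equal variances, complete data, and 0.59 used as the adjacent follow-up correlation. The sample-size arithmetic uses 0.59 as the correlation with baseline, so carrying it over is itself an assumption. Class-series clustering was left out of the calculation.

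The reach is the maintenance models of Objectives 1 to 3. Single-visit contrasts from the 6/12-week model are exposed only if the variance differs between visits. The change is worth making because it is cheap and is right under every pattern in the table.

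**What to change.** In 9.6.1, replace the participant random intercept with an unstructured within-participant covariance over visits (a separate variance for each visit and a separate correlation for each pair), and keep the random effect for class series. Apply this to the maintenance models of Objectives 1 to 3 and, for consistency, to the 6/12-week models, which also protects the 6-week closed test in 9.6.2. Name a fallback for non-convergence: heterogeneous Toeplitz, or robust standard errors with the level of clustering stated. Settle the wording before the study-wide unblinding described in 9.3.

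The cost is SAP text plus a few parameters. The two-visit model goes from 2 to 3 within-participant parameters, and the three-visit model from 2 to 6, estimated from roughly 180 to 204 women at the retention the plan expects (240 × 0.75 to 240 × 0.85). If correlation does decay, the interval for the 12-to-36-week contrast becomes slightly wider.

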To evaluate the efficacy of a group-based yoga intervention for urinary incontinence in ambulatory middle-aged and older women and explore potential mediators of intervention effects in this population.

Study Design

Randomized, multicenter, parallel-group trial of a 12-week yoga intervention versus non-specific muscle stretching/strengthening control intervention for ambulatory women aged 45 years and older with urinary incontinence.

Sample Size and Population

Two hundred fifty women aged 45 years and older who document stress-, urgency-, or mixed-type incontinence occurring at least once per day, are not participating in other organized yoga or muscle stretching/strengthening activities, are temporarily willing to forgo other established clinical treatments for incontinence, and meet minimum mobility and other clinical eligibility criteria, recruited from multiple locations in northern California.

Interventions and Duration

Participants will be randomized in a 1:1 ratio to participate in either a 12-week yoga program (N~120) or a time-equivalent non-specific muscle stretching/strengthening control program (N~120). Women randomized to the yoga program will take part in twice weekly group yoga classes focusing on Iyengar/alignment-based yoga techniques and practice yoga at home for at least one hour per week for 12 weeks. Women randomized to the control program will take part in twice weekly group classes focusing on non-specific muscle stretching/strengthening exercises and practice these exercises at least one hour per week at home for 12 weeks.

Study Outcomes

The primary outcome is change in the frequency of any urinary incontinence episodes between baseline and 12 weeks, measured using validated voiding diaries. Secondary outcomes include changes in the frequency of stress-type, urgency-type, daytime, and nighttime incontinence episodes (also measured by voiding diaries), as well as changes in incontinence-related functioning or quality of life (measured by validated questionnaires), between baseline and 12 weeks. Additional secondary outcomes include persistence of changes in incontinence frequency and condition-specific quality of life 12 and 24 weeks after the end of the intervention programs.

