6.1.6 Cardiac Autonomic Function Measures

To guide exploration of changes in autonomic nervous system function as a potential mediator of intervention effects in women with incontinence, participants will undergo the following measures at baseline and 12 weeks. During the COVID-19 pandemic, participants may decline to undergo these measurements that require them to come into close proximity (less than 6 foot distance) with study personnel.

- A. High frequency heart rate variability (a.k.a. respiratory sinus arrhythmia, or RSA) refers to the degree to which heart rate accelerates and decelerates during the respiratory cycle, and has been shown to be a reliable marker of cardiac parasympathetic activity.⁷¹⁻⁷³ Evaluation of rest-to-stress changes in RSA allows for assessment of abnormalities in adaptive vagal regulation, previously shown to be associated with bladder instability and urine leakage in response to stressful events.²⁰⁻²² Procedures for assessing RSA, monitoring data quality, and interpreting findings have been designed by co-investigator [name], who has authored one of the main textbooks on autonomic assessment,⁷⁴ published four methodological articles and chapters on this topic,⁷⁵⁻⁷⁸ and collaborated with the research team on other NIH-funded studies.⁷⁹ Heart rate variability measurements will be obtained according to standard protocols from the North American Society of Pacing & Electrophysiology,⁸⁰ in which two ECG electrodes will be attached to each participant's right and left wrists using pre-gelled sensors while in the seated position. Following an initial 10-minute "resting" recording, a 10-minute "stress" recording will be obtained while the participant completes two stress tasks, including a visual attention and tracking task⁸¹ shown to reliably induce vagal

withdrawal in subjects across the lifespan.^{75,76} Analyses using Mindware software will examine both resting and rest-to-stress change in RSA.

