9.6.2 Other analytic issues

Participant dropout (i.e., early termination or loss-to-follow-up). Participant dropout levels are expected to be <15% at 12 weeks of intervention, <20% at 12 weeks post-intervention follow-up, and <25% at 24 weeks post-intervention follow-up, assuming a similar rate of attrition over time. The assumption of non-informative dropout will be assessed by comparing baseline characteristics and early post-randomization outcomes of dropouts vs. non-dropouts. If dropout rates differ between groups, sensitivity analyses to evaluate the effects of participant dropout on estimates of intervention effects may be run using inverse probability of retention weights, which can legitimately include post-randomization variables associated with dropout. Alternately or in addition to this, we may use multiple imputation of missing outcomes under plausible informative missingness assumptions.¹⁰⁴

Dose effects (length of exposure and intensity of practice). In the event that the primary analysis shows that yoga intervention is effective in reducing incontinence frequency over 12 weeks, we may use a closed test procedure to assess for dose response in length of intervention exposure without inflating type-I error.¹⁰⁵ Specifically, if we detect a statistically significant benefit over 12 weeks an alpha of 0.05, we may assess change from baseline to 6 weeks, and from 6 weeks to 12 weeks, also at alpha of 0.05, based on contrasts that can be obtained from the primary analysis model. In exploratory analyses, we may also examine whether cumulative hours spent in group intervention classes (based on class attendance logs), or total hours of home yoga or stretching/strengthening practice (documented by participants' home practice logs), are associated with changes in incontinence frequency or secondary outcomes in each group. After the end of the 12-week intervention, additional exploratory analyses may examine associations between continued yoga or control intervention practice (based on continued home practice hours) and maintenance of intervention effects.

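### As worded, the primary contrast across 6 and 12 weeks estimates the change in effect after week 6, not the 12-week effect the trial is designed to test

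*Combined protocol and SAP*

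**What the plan says.** Under Objective 1, section 9.6.1 fits a linear mixed model to change since baseline at two visits, 6 and 12 weeks. Baseline frequency is a covariate, and the time-by-intervention term gives each visit its own effect. The summary rule is: "The intervention effect will be summarized by an orthogonal contrast capturing any linear trend across 6 and 12 weeks". The reason given is that women with a 6-week but no 12-week diary then contribute. No weights are stated, and baseline is not named as a point on the trend.

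The target elsewhere is the effect at 12 weeks:

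- Précis, Study Outcomes: "The primary outcome is change in the frequency of any urinary incontinence episodes between baseline and 12 weeks".
- Section 9.5.1: "The primary efficacy outcome will be change in the average frequency of any urinary incontinence over 12 weeks".
- Section 9.2: "the team will power the study to detect a between-group difference in reduction in incontinence of at least 20" percent, at 3 months.

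Section 9.6.2 (Dose effects) adds follow-on tests, to be used only if the 12-week benefit is significant: "we may assess change from baseline to 6 weeks, and from 6 weeks to 12 weeks, also at alpha of 0.05".

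The approach is reused for other outcomes. For stress and urgency incontinence (Objective 2) the plan says "again using the modeling approach indicated above", and for the mediators (Objective 4) "Intervention effects will first be estimated using LMMs, using the same modeling strategy used for objectives 1-3". Section 6.1.6 states that for the autonomic measures "participants will undergo the following measures at baseline and 12 weeks". Section 6.1.7 and the table in 6.2.7 give the same two visits for pelvic floor strength.

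**The concern.** This sentence turns a model with two treatment effects into one primary result. Followed as written, it asks whether the yoga effect grew between weeks 6 and 12, which is not Hypothesis 1A. A benefit that appears early and is sustained is a good result for patients, but the formal test would tend to miss it. The model would still show the two separate effects, so the benefit would not be hidden.

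The literal contrast also coincides with the 6-to-12-week test that section 9.6.2 reserves for after a positive primary result, so the closed procedure would be circular. For RSA, PEP and pelvic floor strength, which have no 6-week measurement, a trend across 6 and 12 weeks cannot be computed at all. If the wording stays open, the choice between the two quantities could be made after unblinding at the 12-week lock.

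**Working it through.** **Contrast.** Let d6 and d12 be the between-group differences in change from baseline at 6 and 12 weeks. Centring the times gives the linear weights:

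- {6, 12}: (-1, +1), so the contrast is d12 − d6.
- {0, 6, 12}: (-1, 0, +1). Change at baseline is zero, so the contrast is d12.
- {12, 24, 36}, the maintenance analysis: (-1, 0, +1), so d36 − d12, which suits a question about persistence.

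Only the second version matches the primary target, and it needs a baseline point that the sentence does not include.

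**Inputs from section 9.2.** Baseline 23–24 episodes per week; SD of change 14.4; correlation between outcome values 0.59; 15% loss; 120 per arm; two-sided 5%. Completers per arm: 120 × 0.85 = 102. Target difference: 20% of baseline, which is 4.6 at 23 and 4.7 at 23.5.

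**The plan's own figure.** Baseline-adjusted SD = 14.4 × √(1 − 0.59²) = 11.63. For a difference of 4.6 and 80% power this needs 101 per arm, and 101/0.85 rounds up to 119, so N = 238 against the stated 240. With 102 per arm, SE = 11.63 × √(2/102) = 1.628, and the power for d12 is 80.7% at 4.6 and 82.3% at 4.7. The stated sample size therefore matches a test of d12.

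**Power of the literal contrast.** Two inputs are assumptions: the share of the effect present at week 6, and the use of 0.59 as the correlation between the 6- and 12-week changes. Class clustering is ignored.

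SD of the 6-to-12-week difference = 14.4 × √(2 × (1 − 0.59)) = 13.04. Baseline adjustment leaves it unchanged if baseline relates equally to both visits. SE = 13.04 × √(2/102) = 1.826.

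| Share of effect at week 6 | d12 − d6 | Power, literal contrast | Power, d12 |
|---|---|---|---|
| 0% | 4.70 | 73% | 82% |
| 25% | 3.525 | 49% | 82% |
| 50% | 2.35 | 25% | 82% |
| 75% | 1.175 | 10% | 82% |
| 100% | 0 | 5% | 82% |

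At a 50% share, a correlation of 0.4 gives 19% and 0.8 gives 45%.

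**Other ways to place the 0.59.**

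- *Between raw counts at all visits.* SD per visit = 14.4/√0.82 = 15.90, and the SD of the 6-to-12-week difference is 14.4. The literal contrast has 65/42/21/9/5% for the same shares. The adjusted week-12 SD is 12.84, giving 74% for d12.
- *Between baseline-adjusted changes (SD 11.63), with a difference of 4.6.* The literal contrast has 87.7% at 0%, 34.5% at 50%, 12.2% at 75% and 5.0% at 100%, against 80.7% for d12. At a 50% share, correlations of 0.4 to 0.8 give 25% to 61%.

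**Women with only a 6-week diary.** They inform d12 through the mixed-model likelihood, without any trend contrast. Assuming 9 such women per arm and a residual correlation of 0.37, the SE of d12 falls from 1.628 to 1.619.

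**The case against.** The best defence is that the rest of the plan already settles the target. Sections 9.2 and 9.6.2 both attach the 5% level to benefit at 12 weeks. Section 9.6.2 treats baseline-to-6 and 6-to-12 as parts of a larger effect, which makes no sense if the primary test is itself the 6-to-12 part. Change since baseline is zero at baseline by construction, so a trend anchored there gives d12. On this view the defect is an omitted reference to baseline, and a later claim based on d12 − d6 would be hard to defend. For measures without a 6-week visit, an analyst would simply use the week-12 difference.

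Much of this stands as evidence of intent: the authors very probably meant a baseline-to-12-week effect. It does not repair the sentence. The next contrast in the same paragraph runs across 12, 24 and 36 weeks and calls these three time points, so baseline is not counted there. Read the same way, the primary contrast has two points.

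It also stands that the power loss depends on unknown inputs. If the whole effect arises after week 6, and 0.59 applies to the baseline-adjusted changes, the literal contrast (87.7%) has more power than d12 (80.7%). Finally, women with only 6-week data add little precision to d12, about 0.6% of the SE, so that reason for the contrast carries little weight under either reading.

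**Conclusion.** The concern holds. As written, the primary summary is d12 − d6, which is neither Hypothesis 1A nor the quantity for which the trial was sized. The algebra needs no assumptions.

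The cost of following the sentence does depend on assumptions. With half the effect present at week 6, power is about 25% (19–45% for correlations of 0.4 to 0.8; 21–35% across the three placements of 0.59 worked above). With all of it present, power is 5% in every version. The week-12 difference has 81–82% on the basis that reproduces the plan's sample size, or 74% if 0.59 refers to raw counts at every visit.

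This is most likely a drafting error. The model, the data and N = 240 are unaffected, and both effects remain estimable. It must still be corrected, because it governs the formal primary test and is carried over to the secondary and mediator analyses.

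**What to change.** Replace the contrast sentence in section 9.6.1 with wording such as:

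> The primary intervention effect is the between-group difference in mean change from baseline at 12 weeks, estimated from the LMM, with a 95% confidence interval and a two-sided test at the 0.05 level.

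Then:

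- Report the 6-week difference as secondary.
- Keep the 6-to-12-week contrast only within the closed procedure of section 9.6.2.
- State that outcomes measured only at baseline and 12 weeks (RSA, PEP, pelvic floor strength) use the week-12 difference.

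Stating contrast weights that include baseline, (-1, 0, +1) over 0, 6 and 12 weeks, would give the same primary quantity, but naming the difference directly is clearer. Women with only a 6-week diary still contribute through the likelihood.

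The cost is one or two sentences of analysis text before the 12-week dataset is locked, with no change to the model, data collection or sample size.
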